**Intraocular pressure and ocular biometrics changes after phacoemulsification in
glaucomatous patients and age matched controls, comparative study**

September 14th, 2019

Full Protocol

Background and introduction

Phacoemulsification is one of the most commonly performed surgeries in ophthalmic practice. One of the main topics of interest regarding phacoemulsification is its effect on intraocular pressure (IOP) readings whether in glaucomatous or non-glaucomatous eyes by comparing the IOP changes before and after surgery.^{1,2}

The effect of phacoemulsification on ocular biometrics as the depth of the anterior chamber (ACD) has been previously studied³. It showed significant results especially in cases of thick lenses or preoperatively shallow anterior chamber (AC) or narrow AC recess as in cases of angle closure glaucoma².

Changes in the AC angle configuration and the angle opening distance at 500 microns (AOD 500) before and after phacoemulsification have also been studied³. AOD 500 is defined by UBM as the distance of a perpendicular from the trabecular meshwork on the iris at a point 500 µm from the sclera spur⁴. In primary angle closure glaucoma patients even a clear lens extraction showed a significant increase in AOD 500 after phacoemulsification⁵. However, there is no clear evidence whether preoperative ocular biometrics could predict the amount of this IOP reduction after phacoemulsification and whether further filtering surgeries or medications will be still needed for IOP control.

Some studies have shown a significant decrease in IOP after phacoemulsification⁶, with the effect being more significant and the rate of decrease higher the narrower the angle⁷. However, other studies stated that there's a rise of IOP after cataract removal⁸ in the first week and it subsides later on. Another study actually proposed there's no

correlation between phacoemulsification and the IOP pre and postoperatively.⁹ Some studies that stated that there's lowering of IOP after phacoemulsification also showed that filtering surgery was eventually needed in the vast majority of glaucomatous cases and in few of them only cataract removal was sufficient. ¹⁰

This study aims to evaluate the changes in IOP and anterior segment parameters represented by the central ACD and the AOD 500 measured by UBM before and after phacoemulsification.

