In our study we aim to establish a qualitative as well as quantitative relationship between phacoemulsification and the IOP. Also we aim at studying this relationship in non-glaucomatous eyes, open-angle and closed-angle glaucomatous eyes(only appositional type, not synechial angle closure). We want to correlate these changes to the changes in ACD and AOD at 500 pre and postoperatively to establish a quadruple relationship between phacoemulsification on one hand, and the percentage of IOP change ,ACD change and AOD at 500 change on the other hand to study the effect in various eyes and a wide spectrum of the population to earn more accurate results than previous studies.

Patients and methods

An estimation of sample size was performed considering a confidence level of at least 80% with an alpha error of 0.05. On the basis of this estimation, a total of 46 patients was considered adequate. We will include 60 patients taking into account the possibility of drop-outs in the postoperative follow up period.

This is an observational, comparative, cross sectional study that will be conducted at Kasr Alainy Cairo University Hospitals. Data collection will adhere to the tenets of the Declaration of Helsinki. Written informed consent will be obtained from all participants. Patients will be recruited from the glaucoma subspecialty and general outpatient clinics if they fulfill the following criteria; Age 40-70 years, visually significant cataracts with best-corrected visual acuity (BCVA) equal to or worse than 6/12, patients candidates for standard cataract surgeries without adjunctive procedure (e.g., pupil stretching or iris hooks). Exclusion criteria include (1) Major intraoperative orpostoperative complications from cataract surgery; (2) Peripheral anterior synechiae (PAS) detected by indentation gonioscopy; (3) Uveitis, severe retinal diseases, or congenital Anomalies, (4) History of ocular trauma or any intraocular Surgery

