In addition to the routine full ophthalmological examination (Visual Acuity, Auto-refractometer, Slit lamp and fundus examination). All patients meeting the inclusion criteria will have the angle of the anterior chamber assessed by indentation gonioscopy preoperatively to detect whether the angle is opened or closed and to exclude the presence of peripheral anterior synechiae. Also intraocular pressure will be measured using a calibrated Goldman Applanation Tonometry postoperatively. Anterior Chamber Depth & lens thickness will be measured by Optical Biometry (lenstar 900) as well as measurement of the angle & lens vault using the Ultrasound Biomicroscopy (UBM) before and 1 month after cataract surgery. IOP will be measured pre- & postoperatively on day 7 and 30.

Statistical analysis plan:

All data will be entered into Excel spreadsheets (Microsoft Corporation, Redmond, WA, USA). All statistical analyses will be performed using IBM SPSS version 22.0 software (IBM Corp., Armonk, NY, USA). Descriptive statistics will be summarized as the mean \pm standard deviation for numerical data, frequencies and percentages for categorical data. The ANOVA -test and Pearson moment correlation will be used to compare the means for the numerical data and to identify correlations between them. Chi-square test will be used to compare categorical data. P-values ≤ 0.05 will be considered statistically significant.

References

- 1) MelanciaD,Abegao-Pinto L,Marquez-Nevez C:Cataract Surgery and intraocular pressure;J Ophthalmic Research 2015;53:141–148
- 2) Hsu C-H, Kakigi CL, Lin S-C,Wang Y-H, Porco T, Lin SC. Lens position parameters as predictors ofintraocular pressure reduction aftercataract surgery in nonglaucomatouspatients with open angles. Invest Ophthalmol Vis Sci. 2015; 56:7807–7813.
- 3) Ufuk Elgin, EmineSen,TulaySimsek, Kemal Tekin and PelinYilmazbas: Early postoperative effects of cataract surgery on anterior segment parameters in open-angle glaucoma and pseudoexfoliationglaucoma;Turk J Ophthalmol. 2016 Jun;46(3)95-98.
- 4) Martha Kim , Ki Ho Park, Tae-Woo Kim, Dong MyungKim:Changes in Anterior Chamber Configuration after Cataract Surgery as Measured by Anterior Segment Optical Coherence Tomography;Korean J Ophthalmol 2011;25(2):77-83.

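### No reader is named and no masking is planned for the UBM angle measurement, so reader expectation could bias both the comparison of AOD 500 change and its correlation with IOP change

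*Combined protocol and SAP*

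**What the plan says.** The aim at the end of Background and introduction is to evaluate "changes in IOP and anterior segment parameters represented by the central ACD and the AOD 500 measured by UBM before and after phacoemulsification". The same section defines AOD 500 as "the distance of a perpendicular from the trabecular meshwork on the iris at a point 500 µm from the sclera spur".

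The aims then name three kinds of eye: "non-glaucomatous eyes, open-angle and closed-angle glaucomatous eyes(only appositional type, not synechial angle closure"). They also set out the planned correlation of the IOP changes: "We want to correlate these changes to the changes in ACD and AOD at 500 pre and postoperatively". AOD 500 change is therefore both an outcome compared between groups and one side of a correlation.

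The only text on how the angle is imaged for the study is in Patients and methods: "measurement of the angle & lens vault using the Ultrasound Biomicroscopy (UBM) before and 1 month after cataract surgery". The same paragraph places indentation gonioscopy before surgery, to class the angle as open or closed, and IOP before surgery and on days 7 and 30. It does not say who acquires or reads the UBM, when the landmarks are placed, what the reader knows at that moment, or whether images are kept. Masking is not mentioned anywhere, and neither is open reading.

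The Statistical analysis plan names ANOVA and Pearson correlation for numerical data.

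**The concern.** Three features meet here.

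- **The measurement takes judgement.** The reader has to find the scleral spur on an ultrasound image, move 500 µm from it and measure a perpendicular to the iris.
- **The information that could sway the reader arises on the same schedule.** Angle status is known from gonioscopy before surgery. The recruiting clinic ("Patients will be recruited from the glaucoma subspecialty and general outpatient clinics") hints at the diagnosis. The day-30 IOP falls at about the same time as the 1-month UBM.
- **The background sets up expectations.** It reports that AOD 500 rises after lens extraction in angle closure. Of the IOP fall, it says that some studies found it "with the effect being more significant and the rate of decrease higher the narrower the angle".

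A reader aware of the diagnosis or of the IOP fall could, without intending to, place the postoperative landmarks in the expected direction. The result would look like a group difference in AOD 500 change, or like a link between angle opening and IOP reduction. These are two of the relationships that the study sets out to describe. Once values have been recorded in this way, neither ANOVA nor Pearson correlation can separate reader bias from a true effect. Without stored images, the measurement cannot be repeated.

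**Working it through.** **No figure in the plan to reproduce.** The documents give no SD, reader error or effect size for AOD 500, and no group sizes. The stated sample sizes (46 adequate, 60 to be enrolled) do not depend on masking. What can be checked is which kinds of bias reach the planned results, and how test error rates respond to an assumed bias.

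**1. Which bias matters.** Let the reader's shift be b0 at baseline and b1 at 1 month. The observed change is the true change plus (b1 − b0).

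- If b1 = b0, the shift cancels, even when its size differs between groups.
- The group comparison is biased only if (b1 − b0) differs between groups.
- The correlation is biased if (b1 − b0) moves with the IOP change. Postoperative IOP cannot influence a baseline reading made before surgery, so knowledge of it would act on b1 alone and would not cancel.

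**2. Group comparison (illustration).** Assumed inputs:

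- n = 20 eyes per group (60 enrolled ÷ 3 groups, if equal in size, one eye per patient and no losses)
- SD of AOD 500 change 0.06 or 0.08 mm
- reader-induced difference in change, δ, of 0.02, 0.03 or 0.05 mm
- no true difference

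For a two-sample t-test at two-sided 0.05, df = 38 and the critical value is 2.024. The noncentrality is δ / (SD × √(2/20)). For δ = 0.02 and SD = 0.06 this is 0.02 / (0.06 × 0.3162) = 1.054. The three-group ANOVA column shifts one group by δ, with noncentrality 60 × (δ/SD)² × 2/9.

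| SD (mm) | δ (mm) | Noncentrality (t) | Significant, t-test | Significant, three-group ANOVA |
|---|---|---|---|---|
| 0.06 | 0.02 | 1.054 | 17.7% | 17.0% |
| 0.06 | 0.03 | 1.581 | 33.8% | 33.7% |
| 0.06 | 0.05 | 2.635 | 72.8% | 76.0% |
| 0.08 | 0.02 | 0.791 | 12.0% | 11.4% |
| 0.08 | 0.03 | 1.186 | 21.2% | 20.5% |
| 0.08 | 0.05 | 1.976 | 48.7% | 49.9% |

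With δ = 0, every entry is 5%.

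**3. Correlation (illustration).** Suppose that true AOD 500 change is unrelated to IOP change, but the reading moves by b SDs for each SD of IOP change. The induced correlation is r = b / √(1 + b²). The chance that it is significant follows from Fisher's z, with mean atanh(r) × √(N − 3). For b = 0.3 and N = 60, r = 0.3 / √1.09 = 0.287, the mean is 2.23, and the chance is Φ(2.23 − 1.96) ≈ 61%.

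| Assumed b | Induced r | N = 60 | N = 46 |
|---|---|---|---|
| 0.2 | 0.20 | 32% | 26% |
| 0.3 | 0.29 | 61% | 49% |
| 0.5 | 0.45 | 95% | 88% |

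Both tables show how sensitive the tests are to an assumed bias. They are not evidence that bias of this size would occur.

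**The case against.** **Silence is not open reading.** A reader might infer that the scans will be measured openly by staff who know the diagnosis and that day's IOP. The documents do not support this. They do not say who reads the UBM, whether the reader sees the chart, whether IOP is taken first, or whether the two fall on the same day. What stands is that nothing in the plan prevents it.

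**Cost.** One might also infer that masked reading comes free, from stored images and existing staff. Image storage, number of readers and staffing are not described, so feasibility is an assumption.

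**Cancellation.** A reader's habit tied to diagnosis and equal at both visits drops out of the change. This is right, and it narrows the concern to bias that differs by visit and group or follows the IOP change.

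**Expectation.** The narrower-angle statement concerns IOP, not AOD 500. The background also cites an early IOP rise and a study that found no relationship, so it does not point only one way. It does, however, report an AOD 500 increase in angle closure, which is enough to create an expectation for that group.

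**Size.** Every offset and SD above is assumed. This is a fair limit on the numbers, but it does not remove the route to bias.

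**Imperfect remedy.** Lens removal, and perhaps a closed angle, may be visible on the scan (general reasoning, not from the documents). Masking would then be incomplete. Withholding IOP would still cut the most direct route to a spurious correlation.

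**Conclusion.** The concern holds as a gap in the plan. AOD 500 depends on landmark placement and enters two main results, yet the protocol names no reader and has no step that masks the reader to diagnosis, gonioscopy or IOP. The plan as written therefore leaves open an avoidable route to bias. Only expectation that differs by visit and group, or that follows the IOP change, would pass into those results.

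The size is unknown. Under the assumed inputs, the false-positive rate of the two-group comparison rises from 5% to between about 12% and 73%, and the planned ANOVA behaves similarly. The documents do not show that such bias will occur. The change should be made before data collection, but the gap does not invalidate the study.

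**What to change.** Add a short paragraph to Patients and methods that covers the following:

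- Who reads the UBM images.
- That images from both visits are saved under a code that shows neither patient nor visit.
- That, after day 30, whoever would otherwise have read them measures AOD 500 in one batch and in random order, with diagnosis, gonioscopy result and IOP withheld.
- That masking is partial, because lens removal and a closed angle may be recognisable on the scan.

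Any angle reading needed for care can still be made at the visit and kept out of the study data. Re-reading a random subset within the batch would be a useful addition, although it measures repeatability and does not remove expectation bias.

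The cost is clerical work for coding and batching, and AOD 500 values that become available only after follow-up. Sample size, visits and procedures do not change. All of this assumes that the UBM images can be stored, which the documents do not state. If they cannot, the protocol should say so, state what the reader knows at each measurement, and list this as a limitation.

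### The aim is change within the same eyes, but the plan names only unqualified ANOVA for means, and the age matching claimed in the title has no method behind it

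*Combined protocol and SAP*

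**What the plan says.** The stated aim is change: "This study aims to evaluate the changes in IOP and anterior segment parameters". The Patients and methods section schedules IOP before surgery and on days 7 and 30, and biometry and angle measurements before and one month after surgery. Each eye is therefore its own control.

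The Statistical analysis plan section gives one sentence for means and correlations: "The ANOVA -test and Pearson moment correlation will be used to compare the means for the numerical data". It does not state the form of the ANOVA, its dependent variable, the time point or the contrast.

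The end of the background describes the comparison in eyes and in three groups, "non-glaucomatous eyes, open-angle and closed-angle glaucomatous eyes", and names the change quantities to be related to each other: "the percentage of IOP change ,ACD change and AOD at 500 change". The sample size is counted in patients: "a total of 46 patients was considered adequate", then "We will include 60 patients taking into account the possibility of drop-outs". There is no rule for one or both eyes.

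The title describes the study as one in "glaucomatous patients and age matched controls". The methods recruit from a glaucoma clinic and general clinics under a single 40 to 70 year range. They describe no matching step, and the analysis has no age term.

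**The concern.** An unqualified ANOVA can be run in ways that respect the pairing of visits and in ways that do not. Ordinary ANOVA on the values at each visit treats before and after as separate samples. It leaves the between-eye spread in the error term, so a real fall in IOP is easier to miss. The methods label the design cross-sectional, which makes it less safe to take a within-eye analysis for granted.

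The groups are not randomised, so age can differ between them by chance or by route of recruitment. The title tells the reader that this has been handled, and nothing in the methods or analysis handles it.

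**Working it through.** **Inputs.** From the documents: 46 patients required, 60 enrolled, three groups in the aims, three IOP visits, two biometry visits, ages 40 to 70, significance at 0.05. Not in the documents, so assumed: two-sided tests, groups of 15/15/16 (46) or 20/20/20 (60), pre/post correlation ρ of 0.3 to 0.7, a mean fall of 0.5 SD, and an IOP SD of 3.5 mmHg. The plan gives no figure of its own to reproduce on this point.

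**1. Cost of ignoring pairing.** For n eyes and a fall of 0.5 SD, the paired test has noncentrality 0.5 × √n / √(2(1 − ρ)). With n = 15 and ρ = 0.5 this is 0.5 × 3.873 / 1 = 1.94, which on 14 degrees of freedom gives power 43.8%. The unpaired standard error is larger by the factor 1/√(1 − ρ), here 1.41. Unpaired power is from 200,000 simulated trials per cell.

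| Eyes | ρ | Visits as independent samples | Paired |
|---|---|---|---|
| 15 | 0.3 | 22.9% | 33.2% |
| 15 | 0.5 | 19.7% | 43.8% |
| 15 | 0.7 | 15.4% | 64.3% |
| 20 | 0.3 | 31.3% | 43.4% |
| 20 | 0.5 | 28.4% | 56.5% |
| 20 | 0.7 | 24.5% | 78.2% |

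The stronger the correlation, the more is lost.

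**2. If both eyes were entered.** A random intercept for patient removes a shared level but not a shared change. With 15 patients, two eyes, three visits and no true visit effect, such a model rejects in about 12%, 17% and 22% of simulated trials at inter-eye correlations of change of 0.3, 0.5 and 0.7. Averaging the two eyes within each patient avoids this.

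**3. Choice of IOP group comparison.** These are simulated false-positive rates with no true group effect, sizes 15/15/16, control baseline 16 mmHg, mean fall 2 mmHg, pre/post slope 0.5 to 0.7, a baseline 3 to 5 mmHg higher in both glaucoma groups, and age in the model.

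| Assumed baseline relation | Percentage change | Absolute change | Day-30 IOP adjusted for baseline |
|---|---|---|---|
| All eyes share one pre/post line | 8–29% | 13–48% | about 5% |
| Stable gap, equal mean fall | 6–8% | about 5% | 14–44% |

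No analysis is safe under both assumptions. Percentage change is not the worst under either. The large rates depend on the assumed gap: at 1 mmHg the rates are about 5–8%. The documents give no baseline IOP.

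**4. Age.** If ages are uniform on 40 to 70, the SD is 30/√12 = 8.66 years. The 95% limit for a chance difference between two groups of 15 is 1.96 × 8.66 × √(2/15) = 6.2 years, and 5.4 years for groups of 20. At an assumed 0.05 to 0.10 mmHg per year, 6.2 years shifts a group difference in IOP change by 0.31 to 0.62 mmHg. The 95% CI half-width for 15 against 16 eyes at ρ = 0.5 is 2.0167 × 3.5 × √(2 × 0.5) × √(1/15 + 1/16) = 2.537 mmHg. The possible shift is small beside it.

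**The case against.** The strongest reply is that ANOVA of per-eye change is the natural reading. The protocol says "We want to correlate these changes to the changes in ACD and AOD at 500", so change scores must be computed anyway, and an ANOVA of those scores respects pairing, as does repeated-measures ANOVA. This stands: under either, the power loss in step 1 disappears. What remains is that the text does not say so.

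A reader might go further and infer that visits will be pooled as independent values to compare groups, which would inflate false positives. Nothing in the analysis section points to that.

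A reader might also infer that both eyes will be entered as independent. The documents do not support this. The sample size is in patients, and the exclusion of earlier intraocular surgery, read per patient, would keep a second eye out after the first operation. That clause could also be read per eye, so a rule is still needed, but the error is not shown.

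On age, it is fair to say that the effect is small. The documents do not show that the groups differ in age, and the calculation gives only a possible imbalance.

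Finally, percentage change is an imperfect primary quantity, as step 3 shows. That is a reason to report the adjusted analysis beside it, not to leave the choice open.

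**Conclusion.** The point holds as a gap between the aim and the named method. The aim is within-eye change, and the plan names no paired or repeated-measures test. If ordinary ANOVA on visit values were used, power for a 0.5 SD fall in a group of 15 would be about 20% instead of 44% at ρ = 0.5, and between 15% and 23% instead of 33% to 64% over ρ from 0.3 to 0.7. Group size, effect and correlation are all assumptions. If ANOVA of change or repeated-measures ANOVA with one eye per patient is intended, the analysis is sound and only the wording needs work.

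The age-matching claim is unsupported by the methods as written. It should be delivered or dropped. The documents do not support a finding of confounding by age.

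This should be fixed before analysis. Confidence is medium, because much of the point concerns detail left unstated.

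**What to change.** Replace the sentence on ANOVA with the following.

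1. The patient is the unit. One eye per patient is analysed, chosen by a stated rule. If both eyes are measured, their values are averaged per patient; a patient-only random intercept is not relied on.
2. Within-group change is tested by repeated-measures ANOVA or a mixed model over the three IOP visits, and by paired tests for ACD and AOD 500.
3. The primary group comparison is percentage IOP change at day 30 across the three groups in the aims (non-glaucomatous, open-angle, appositional closed-angle), by ANOVA with age as covariate, giving differences with 95% CI. ACD and AOD 500 change at one month are compared in the same way as secondary outcomes.
4. Day-30 IOP adjusted for baseline IOP and age is reported as a sensitivity analysis only. Any disagreement with item 3 is stated.
5. The age-matching claim is removed from the title unless a matching step is actually used and described.

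Pearson correlation stays for relating the changes to each other.

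**Cost.** Some SAP text and a little more analysis of measurements already planned; age is already an eligibility item. Age uses one degree of freedom. On the absolute scale the CI half-width moves from 2.537 to 2.539 mmHg (t from 2.0167 on 43 degrees of freedom to 2.0181 on 42), before any overlap between age and group; the cost on the percentage scale was not computed. The real downside is that the two IOP group results may disagree, and both must then be reported. Introducing a matching step would change recruitment, so dropping the term is the cheaper choice.
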